### 7.1.7 Protocol Deviations Because of an Adverse Event

If a patient experiences an adverse event or medical emergency, deviations from the protocol may be allowed on a case-by-case basis. To ensure patient safety, after the patient's condition has stabilized and/or treatment has been administered, the investigator or other physician in attendance must contact the physician identified in the Clinical Study Personnel Contact Information section of this protocol as soon as possible to discuss the situation. The investigator, in consultation with the CRO and sponsor, will decide whether the patient should continue to participate in the study.

### 7.2 Pregnancy

All women of reproductive age who participate in the study will be counseled on the need to practice adequate birth control and on the importance of avoiding pregnancy during study participation. Women will be instructed to contact the investigator or study staff immediately if pregnancy occurs or is suspected. Becoming pregnant during study participation is not considered an adverse event; however, any complications during pregnancy within the course of the study may be considered an adverse event(s).

Innocoll

Clinical Study Protocol With Amendment 02

Study INN-CB-024

Controlled Study-Postsurgical Analgesia

### 7.3 Medication Error and Special Situations Related to the Study Drug

Any administration of the study drug that is not in accordance with the study protocol or surgery manual should be reported on the CRF and in the patient's source documents as a deviation, regardless of whether or not an adverse event occurs as a result.

### 7.4 Clinical Laboratory Tests

Blood and urine samples for clinical laboratory tests will be collected at the screening visit; and blood samples only will be collected at the day-30 follow-up visit (see [Table 1](#)).

#### 7.4.1 Hematology, Serum Chemistry, and Urinalysis

The following clinical laboratory tests will be performed:

Hematology (complete blood count [CBC])	Serum chemistry:	Urinalysis
Hematocrit Hemoglobin Platelet count White blood cell (WBC) count WBC differential (percentage and absolute): – basophils – eosinophils – lymphocytes – monocytes – neutrophils	Blood urea nitrogen Creatinine Total bilirubin Alanine aminotransferase (ALT) Aspartate aminotransferase (AST) Alkaline phosphatase Sodium Potassium Calcium Chloride Phosphate Serum bicarbonate Total cholesterol Glucose (nonfasting) Albumin	Color and appearance Specific gravity pH Ketones Protein Blood Glucose

The following additional laboratory tests will also be performed:

- For women of childbearing potential, a serum sample for pregnancy test will be collected at screening, and a urine sample on the day of surgery (with results available before study-drug kit assignment) and on day 30.

All clinical laboratory test results outside the reference range will be assessed by the investigator as belonging to one of the following categories:

- abnormal and not clinically significant
- abnormal and clinically significant

A laboratory test result that is judged by the investigator as clinically significant will be recorded both on the source documentation and the CRF as an adverse event and will be monitored as

Innocoll

Clinical Study Protocol With Amendment 02

Study INN-CB-024

Controlled Study-Postsurgical Analgesia

described in [Section 7.1](#), whether during or at the completion of participation. An event may include a laboratory or diagnostic test abnormality that results in the withdrawal of the patient from the study, the temporary or permanent withdrawal of medical treatment, or further diagnostic work-up. (NOTE: Abnormal laboratory or diagnostic test results at the screening visit that preclude a patient from entering the study or receiving study drug are not considered adverse events.)

Clinical laboratory tests (serum chemistry, hematology, and urinalysis) will be performed at the time points detailed in [Table 1](#). Blood samples (approximately 16 mL total per patient) will be collected. Clinical laboratory tests will be performed using the central laboratory.

#### 7.4.2 Urine Drug Screen

A urine drug screen will be performed at the screening visit and immediately before surgery (see [Table 1](#)). Urine screening will be done for drugs of abuse/misuse, with testing during the screening period and on the day of surgery (with results available before study-drug kit number assignment).

A positive result for any excluded drugs of misuse/abuse (see [Section 4.2](#)) or their metabolites without medical explanation will preclude the patient from enrollment or continued participation in the study.

#### 7.5 Vital Signs

Vital signs, including body temperature, pulse, systolic and diastolic blood pressure, respiration rate, and oxygen saturation, will be measured/recorded at screening, preoperatively, and at the following posttreatment time points: 0.5 hours ( $\pm 5$  minutes); 1, 2, 4 hours ( $\pm 15$  minutes); 8, 12 hours ( $\pm 2$  hours); 24, 48, 72 hours ( $\pm 4$  hours) prior to discharge; day 15 ( $\pm 3$  days); and day 30 ( $\pm 3$  days) (see [Table 1](#)).

Oxygen saturation will be monitored by pulse oximetry during the inpatient study period. Oxygen saturation will be recorded at the individual time points listed above. Pulse oximeter alarms should be set according to clinic standards, with oxygen desaturation that occurs in concordance with the delay period and the specified limits recorded as an adverse event. Patients should be evaluated to ensure proper pulse oximeter placement and to ensure desaturation is not due to patient movement or device-related issues.

All vital sign results outside the reference ranges will be judged by the investigator as belonging to one of the following categories:

- abnormal and not clinically significant
- abnormal and clinically significant

#### 7.6 Physical Examinations

A complete physical examination will be performed at screening and on day 30 ( $\pm 3$  days) after treatment (including screening body weight and height and posttreatment weight only) (see [Table 1](#)). A complete physical examination will include at a minimum skin, lungs, CV, respiratory, gastrointestinal, musculoskeletal, and neurological assessments. Any physical examination finding that is judged by the investigator as clinically significant (except at the screening visit) will be considered an adverse event, recorded in the CRF, and monitored as

Innocoll

Clinical Study Protocol With Amendment 02

Study INN-CB-024

Controlled Study-Postsurgical Analgesia

described in [Section 7.1.2](#). Investigators should pay special attention to clinical signs related to previous serious diseases.

### **7.7 Electrocardiography**

A standard 12-lead ECG will be performed locally (by a physician [ie, the investigator or subinvestigator]) and recorded (after the patient has been supine for at least 5 minutes) at screening and on day 30 ( $\pm 3$  days) (see [Table 1](#)). All ECG recordings will be identified with the patient number, date, and time of the recording.

All ECG results outside of the reference ranges should be evaluated and will be judged as belonging to one of the following categories:

- abnormal and not clinically significant
- abnormal and clinically significant

Any ECG finding that is judged as clinically significant (except at the screening visit) will be considered an adverse event, recorded on the source documentation and on the CRF, and monitored as described in [Section 7.1.2](#).

Innocoll

Clinical Study Protocol With Amendment 02

Study INN-CB-024

Controlled Study-Postsurgical Analgesia

---

**8 ASSESSMENT OF PHARMACOKINETICS: NOT APPLICABLE**

Pharmacokinetics are not assessed in this study.

Innocoll

Clinical Study Protocol With Amendment 02  
Study INN-CB-024

Controlled Study-Postsurgical Analgesia

## **9 STATISTICAL METHODS**

This section describes the statistical analysis as foreseen at the time of planning the study. Changes, additions, and further details about the analyses will be described in the statistical analysis plan (SAP). After finalization of the SAP, any additional analyses or changes to analyses that may be required will be fully disclosed in the clinical study report (CSR).

### **9.1 Sample Size and Power Considerations**

The sample size was chosen primarily on the basis of previous clinical study data for INL-001 in inguinal hernia repair, but also with the consideration of the results of other bupivacaine-containing products studied in abdominoplasty. Sample size is estimated at 360 patients, with 180 patients per treatment group. The effect size with INL-001 in the combined results of 2 clinical Phase 3 studies in postoperative analgesia after open inguinal hernia repair was 0.525 for SPI24. The effect size with INL-001 for SPI48 was 0.25. With the historical SPI48 effect size of 0.25, 360 evaluable patients will yield a power of at least 66%; however, it is believed that a greater separation between the INL-001 and placebo treatment groups will be observed for abdominoplasty given that postoperative pain is more severe and longer lasting than with inguinal hernia repair, yielding greater power. This is increased to 372 patients to potentially counter the effects of imputation for dropouts, but all randomized and treated patients will be evaluable and included in the modified intent-to-treat (mITT) analyses.

### **9.2 Analysis Sets**

#### **9.2.1 Intent-to-Treat Population**

The intent-to-treat (ITT) population will consist of all patients randomly assigned to study treatment who may or may not have received any dose of study drug (INL-001 or placebo collagen implants). The ITT population will be used mainly for disposition patient-count purposes. Following the ITT principle, data from patients will be analyzed according to assigned treatment at randomization.

#### **9.2.2 Modified ITT Population**

The mITT population will consist of all patients randomly assigned to study treatment who receive any dose of study drug. Following the ITT principle, data from patients will be analyzed according to their assigned treatment at randomization. The mITT population will be the primary population for efficacy assessments.

Innocoll

Clinical Study Protocol With Amendment 02

Study INN-CB-024

Controlled Study-Postsurgical Analgesia

### **9.2.3 Safety Analysis Set**

The safety population will consist of all patients who receive any dose of study drug. Data will be analyzed according to treatment received. The safety population will be used for safety analyses.

### **9.2.4 All Patients**

All patient data entered into the electronic data capture system will be used for the patient disposition displays and may include data from patients who did not meet screening criteria.

### **9.3 Data Handling Conventions**

For all variables other than SPI, only the observed data from the patients will be used in the statistical analyses, ie, there is no plan to estimate missing data, unless otherwise specified. If conducted, detailed data imputation rules will be described in the SAP.

See [Section 9.5](#) concerning SPI scores for the handling of missing data and rescue medications.

### **9.4 Study Population**

The safety analysis set (see [Section 9.6](#)) will be used for all study population summaries unless otherwise specified. Summaries will be presented by surgery type and for all patients.

#### **9.4.1 Patient Disposition**

Data from patients screened; patients enrolled; patients enrolled but not treated; patients in the safety, ITT, and mITT analysis sets; patients who complete the study; and patients who withdraw from the study will be summarized using descriptive statistics. Data from patients who withdraw from the study will also be summarized by reason for withdrawal using descriptive statistics.

#### **9.4.2 Demographic and Baseline Characteristics**

Patient demographic and baseline characteristics will be summarized using descriptive statistics. For continuous variables, descriptive statistics (number [n], mean, standard deviation [SD], median, minimum, and maximum) will be provided. For categorical variables, patient counts, and percentages will be provided. Categories for missing data will be presented, if necessary. Patients will be stratified by study center and BMI (<30 kg/m^2 and ≥30 kg/m^2).

### **9.5 Efficacy Analysis**

The estimand for the primary efficacy endpoint will use a hypothetical strategy. Intermittent missing values will be assumed to fall along a line connecting the observed values on either side of the missing value. For the intercurrent event of rescue medication, patients will have their pain recorded just prior to the administration of rescue medication; to estimate what the pain values may have been had the rescue not been administered, if all values are less than the pain score recorded just prior to administration of rescue medication, then the values collected during the period (4 hours) of efficacy of the rescue medication will be replaced with values falling on a line connecting the pain score recorded just prior to rescue medication administration to the first pain score outside the duration of efficacy of the rescue medication. However, pain scores that

Innocoll

Clinical Study Protocol With Amendment 02  
Study INN-CB-024

Controlled Study-Postsurgical Analgesia

are equal to or greater than the score measured just prior to administration will be included in the calculation. For the intercurrent event of discontinuation, data for patients who discontinue the study for lack of efficacy and for adverse events will be assumed to follow the distribution of the worst values observed to the point of withdrawal; data for patients withdrawing for other reasons will be assumed to follow the distribution of the values in their treatment group.

The SPI (AUC of pain intensity as measured by the NPRS) through various time points up to 72 hours posttreatment will be calculated using the trapezoidal method with NPRS scores and the actual assessment times in hours. The primary efficacy variable will be SPI24, but the same general rules and calculations will apply for all SPI0-time. For SPI24 calculation, both scheduled and unscheduled values (if available) from Time 0 through 24 hours posttreatment will be used in the calculation. For patients who receive rescue medication, just prior to it being administered, a pain score will be obtained; this will be included in the calculation of the SPI. Pain score(s) for the duration of the rescue efficacy following treatment with an opioid rescue medication will be excluded from the calculation if they are lower than the pain score just prior to rescue medication administration; those that are equal to or higher will be included. This period will be 2 hours following iv morphine and 4 hours following oxycodone. Pain scores in this window that are less than the pain recorded just prior to rescue medication administration will be excluded from the calculation, and linear interpolation will be used to connect the pain just prior to rescue medication administration to the first measure outside of 2 or 4 hours after administration of iv morphine or oral oxycodone, respectively.

Assuming a patient has a 24-hour nominal value, their SPI value will be normalized to exactly 24 hours. Should the patient be missing the nominal 24-hour value, but has a subsequent NPRS score recorded, linear interpolation will be performed to impute the 24-hour value by connecting the prior and subsequent values and calculating where the 24-hour value would fall on that line. The previously stated rules around rescue medication use will be applied should the 24-hour value fall within the 2- or 4-hour window of rescue medication use; the NPRS score collected from the associated rescue medication use will serve as the prior point for the imputation and the first subsequent noncensored value will serve as the other anchor. If observed values are greater than or equal to the pre-rescue-medication value (and before the 24-hour cut-off), then they will be used.

If a patient withdraws from the study and does not continue to provide pain assessments or has no values following a missing/censored 24-hour value, multiple imputation methods will be employed using observed data and reason for withdrawal. First, all pain intensity values will be assigned to their nominal time points for the purposes of creating covariates for the multiple imputation; when a rescue medication was used, the scheduled values that fall in the censoring period will be replaced with the “pain right now” collected prior to the rescue use. This substitution will be employed only for executing the multiple imputation (MI) procedure for imputing values after withdrawal; the methods above will be used for the actual SPI calculation. Data for patients who discontinued early due to lack of efficacy or an adverse event(s) will be imputed using the distribution of the worst values observed to that point, conditioned on the nonmissing values. For patients who discontinue for any other reason, values will be imputed assuming missing at random; covariates will include all nonmissing pain-intensity assessments and imputation will be done within treatment group. For the multiple imputation stages, values will be imputed using 20 replicates and the Markov Chain Monte Carlo (MCMC) method implemented with the SAS (Statistical Analysis Software®) MI procedure. Patients who are

Innocoll

Clinical Study Protocol With Amendment 02

Study INN-CB-024

Controlled Study-Postsurgical Analgesia

missing their 0.5-hour and/or 1-hour values will have that value imputed as the first nonmissing value and the SPI will be calculated as described. Full details of the SPI calculations will be in the SAP, including sensitivity analyses to test the robustness of the assumptions.

All efficacy comparisons will be based on the comparison of INL-001 vs placebo.

The primary efficacy variable, SPI24, will be analyzed using an analysis of covariance (ANCOVA) model with treatment as the main effect and a covariate for BMI (continuous). Summary statistics (sample size, mean, SD, median, minimum, maximum, and 25th and 75th percentiles) will be presented along with the least squares (LS) mean, standard error (SE), 95% CIs, difference in LS means, and p-values from the ANCOVA model.

To account for the interim analysis and potential sample size increase, the method of [Cui et al 1999](#) will be employed. For the final analysis and resulting p-value, the data will be split for those patients included in the interim analysis and those not included in the interim analysis; data from these groups will be analyzed completely independently, then combined using the inverse normal method to test the null hypotheses that there is no difference between the treatment groups:

$$Z_1 = \Phi^{-1}(1 - p_1)$$

$$\text{and } Z_2 = w_1 Z_1 + w_2 \Phi^{-1}(1 - p_2)$$

where:

$Z_1$ =the Z statistic for the first stage

$Z_2$ =the combination test statistic at the end of the second stage

$w_i$ =the weighting applied for each associated Z statistic

$p_1$ =the first stage p-value

$p_2$ =the second-stage p-value based on second-stage participants

For maximum statistical efficiency, the weights are defined prospectively according to the square root of the planned proportion of participants in the 2 stages, relative to the preplanned total enrollment of 360 patients, as  $w_i = \sqrt{0.5}$ . The calculation of these weights is fixed and will not be changed due to unblinded data; likewise, in the case of deviations from the planned proportions due to enrollment overrun (see interim analysis section below), the weights will remain fixed.

The key secondary efficacy variables include:

- SPI from Time 0 through 48 hours (SPI48)
- proportion of patients who are opioid free posttreatment through 24 hours
- proportion of patients who are opioid free posttreatment through 48 hours
- SPI from Time 0 through 72 hours (SPI72)
- proportion of patients who are opioid free posttreatment through 72 hours

An approach identical to the primary efficacy analysis will be used for each of the continuous key secondary variables and the same statistics will be presented. For key secondary outcomes of proportions, each proportion, the difference, and 95% confidence intervals (CIs) will be reported; the difference will be tested with the 2-proportion Z test (with Cui-Hung-Wang [CHW] method

Innocoll

Clinical Study Protocol With Amendment 02

Study INN-CB-024

Controlled Study-Postsurgical Analgesia

applied to account for the interim analysis). In the case of low counts (any expected cell count  $\leq 5$ ), a Fisher's Exact test will be used; p-values will be transformed to an equivalent Z for applying the CHW method.

All continuous secondary efficacy variables will be summarized with appropriate descriptive statistics (sample size, mean, SD, coefficient of variation [CV], median, minimum, maximum, and 25th and 75th percentiles) and analyzed using ANCOVA models with treatment as the main effect and a covariate for BMI.

Summary graphs of efficacy data including TOpA and NPRS scores by treatment group (arithmetic means and standard error [SE]) vs nominal time will be plotted.

All categorical efficacy variables will be summarized with counts and proportions and compared by Cochran-Mantel-Haenszel tests (for ordered variables), Pearson chi-squared, or Fisher's exact tests as needed.

The time to first use of opioid rescue medication, time to discharge from the PACU, and time to no longer using rescue medication during the study will be summarized using Kaplan-Meier methods. Log rank tests will be used to compare treatment groups. The median time to discharge will be estimated together with the associated 95% CI.

Models containing additional blocking factors or covariates may be fit as secondary analyses.

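### The multiple-imputation input overwrites every scheduled score in the rescue window, including scores that rose, although the SPI rule in the same section discards only lower scores

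*Protocol*

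**What the plan says.** All of the relevant text is in Protocol section 9.5.

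- **Estimand paragraph.** After rescue, scores that "are equal to or greater than the score measured just prior to administration will be included in the calculation". Patients who discontinue for lack of efficacy or adverse events are "assumed to follow the distribution of the worst values observed to the point of withdrawal".
- **SPI calculation.** Scores in the rescue window are excluded "if they are lower than the pain score just prior to rescue medication administration; those that are equal to or higher will be included". The window is 2 hours after iv morphine and 4 hours after oxycodone.
- **Multiple imputation, first step.** Scores are assigned to nominal times to create covariates, and "when a rescue medication was used, the scheduled values that fall in the censoring period will be replaced with the" score collected before the rescue. No comparison with the pre-rescue score is made.
- **Scope of that step.** "This substitution will be employed only for executing the multiple imputation (MI) procedure for imputing values after withdrawal", and "the methods above will be used for the actual SPI calculation".
- **Multiple imputation, next step.** Data for lack-of-efficacy and adverse-event withdrawals "will be imputed using the distribution of the worst values observed to that point, conditioned on the nonmissing values". Other withdrawals are imputed as missing at random within treatment group, with all nonmissing pain scores as covariates. Both use 20 replicates and MCMC.

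**The concern.** A pain score that rises after rescue is direct evidence that the rescue, and arguably the study treatment, did not control pain. The estimand and the SPI rule both keep such a score. The imputation step, read as written, replaces it with the lower pre-rescue score. The imputation model then works from data that do not follow the plan's own rescue rule.

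The sentence confining the substitution to the imputation step protects only the observed part of the SPI. Values imputed after withdrawal are themselves part of SPI24 (primary) and of SPI48 and SPI72 (key secondary), so whatever is lost in the input can reach the endpoints.

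Two things are at stake. The covariates and within-arm reference data are altered for every patient who is imputed. In addition, on one available reading, the worst values assigned to treatment failures could be taken from data in which their highest scores have been overwritten.

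**Working it through.** The plan states no figure on this point, so the check is a comparison of the rules, an illustration of the mechanism, and a size calculation on assumed inputs.

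**1. The rules side by side**

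| Score in the rescue window | SPI calculation | Imputation input, as written |
|---|---|---|
| Lower than pre-rescue score | Excluded, line drawn from pre-rescue score | Replaced by pre-rescue score |
| Equal to pre-rescue score | Kept | Replaced, value unchanged |
| Higher than pre-rescue score | Kept | Replaced by the lower pre-rescue score |

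The conflict is confined to the last row. The censoring period is a span of time, and the substitution sentence covers the scheduled values in it without exception. Elsewhere in 9.5, where the status of an individual score matters, the text says so by referring to a noncensored value.

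**2. How many scores can be touched.** The scheduled NPRS times through 24 h (section 3.1) are 0.5, 1, 2, 3, 4, 5, 6, 8, 10, 12, 18, 20 and 24 h. For rescue given from 0.5 h on, one oxycodone window covers up to 4 of them (a dose at 2.75 h covers 3, 4, 5 and 6 h). One morphine window covers up to 2.

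**3. Mechanism, with assumed scores.** Oxycodone is given at 5.5 h with a pre-rescue score of 6. Scheduled scores are 8 at 6 h and 9 at 8 h, no earlier score exceeds 6, and the patient withdraws at 9 h for lack of efficacy.

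- Imputation input as written: 6 at 6 h and 6 at 8 h. The highest retained score is 6.
- Input under the SPI rule: 8 and 9. The highest retained score is 9.

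Suppose, for illustration only, that all later values were set to the highest retained score. The observed 9 at 8 h stays in the SPI either way.

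- As written, 8 to 24 h: (9 + 6)/2 × 2 + 6 × 14 = 15 + 84 = 99.
- SPI rule, 8 to 24 h: 9 × 16 = 144.
- Difference: 45 point-hours for this patient.

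Other assumed rising patterns gave 15 to 60 point-hours. When the window scores fell below the pre-rescue score, the difference was 0. The protocol draws from a distribution and does not carry a maximum forward, so these figures show the mechanism and are not an expected effect.

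**4. Size on an arm mean.** The shift is f × d × h, where f is the fraction of the arm that withdraws with an understated worst value, d the understatement in points, and h the hours from withdrawal to 24 h. The protocol gives none of these. The SPI24 scale runs to 10 × 24 = 240.

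- Assume f = 5%, d = 2, h = 12 (withdrawal at 12 h, every withdrawal affected): 0.05 × 2 × 12 = 1.2 point-hours, and 1.2/240 = 0.5% of the scale.
- With the 15 to 60 point-hour patterns of step 3 and the same 5%: 0.05 × 15 = 0.75 to 0.05 × 60 = 3.0, or 0.3% to 1.25% of the scale.

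Both lines take every withdrawal as affected and the full understatement as imputed. They therefore overstate the shift for those inputs.

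**5. Effect on the treatment difference.** Each arm mean would be lowered by its own amount. The difference moves by the gap between the two amounts, and its sign depends on which arm has more failed rescues followed by withdrawal. The protocol gives no rates for either.

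**The case against.** The strongest reply concerns what is meant by worst values. The plan speaks of worst values that were observed. A substituted score was not observed, and the substitution is described as serving to create covariates. On that reading the recorded peak survives for the worst-value step. This stands: a reader might infer that the plan certainly erases a failing patient's worst pain, and the text does not say that. The substitution comes first and nothing states that worst values are taken before it, so the opposite reading is open too. The removal of risen scores from the covariates and within-arm reference data does not depend on this question.

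A reader might also infer that each such patient is owed their own maximum, so that differences such as 45 point-hours are the real loss. The plan imputes from a distribution of worst values, conditioned on nonmissing values, and draws below a patient's own peak are compatible with that.

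Other provisions narrow the case. Section 3.1 requires a score before any rescue, and section 4.3.1 asks for one before standard-of-care analgesia and for continued scoring. A later score will often preserve the peak. Imputation is used only when a patient stops giving scores or has none after a missing or censored 24-hour value.

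It is tempting to add that unscheduled pre-rescue scores drop out of the imputation data when no scheduled time lies in their window. The protocol does not say how unscheduled scores are assigned to nominal times, so this cannot be claimed.

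Section 9.5 leaves full SPI details to the SAP, which is not at hand and may resolve the matter. The protocol nevertheless states an unconditional rule, and a SAP that followed it faithfully would inherit the conflict. The sensitivity analyses in section 9.7 vary the window length and the withdrawal reasons. A shorter window exposes fewer scores, but none of the analyses tests the overwrite itself.

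**Conclusion.** The point holds in a limited form. The substitution sentence conflicts with the estimand and SPI rules in the same section, and followed literally it removes observed scores that rose after rescue from the imputation covariates and reference data. Understatement of worst values for lack-of-efficacy or adverse-event withdrawals is a further consequence only if those values are taken from the substituted data, and only when no other retained score is as high.

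The effect on an arm mean is probably small: about 1.2 of 240 point-hours with 5% withdrawing at 12 h and all understated by 2 points, and 0.75 to 3.0 over the other assumed patterns. These rest on assumed withdrawal rates, times and scores. A reader might infer a bias in favour of INL-001 or an inflated Type I error; the documents support neither. If placebo had more failures, the treatment difference would shrink. The correction is worth making because it concerns the primary endpoint and costs almost nothing.

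**What to change.** In section 9.5, replace the substitution sentence with: *scheduled values in the censoring period that are lower than the pre-rescue score will be replaced with the pre-rescue score; values equal to or higher are kept.* Add: *worst values for patients who discontinue for lack of efficacy or an adverse event are taken from recorded scores, before any substitution.* Carry the same wording into the SAP.

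The cost is two sentences and a small programming change. No new data or patients are needed.
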